#### B. ***Exclusion Criteria***

Subjects must NOT meet any of the following exclusion criteria:

1. Presence of structural heart disease of clinical significance including:
  - a. Coronary artery disease with either:
    - i. Coronary artery bypass surgery (CABG) within the last 180 days (six months), or
    - ii. Stable/unstable angina or ongoing myocardial ischemia.

- b. Congenital heart disease where either the underlying abnormality or its correction prohibits or increases the risk of ablation.
- 2. NYHA Class III – IV.
- 3. Ejection fraction < 40% (within previous six months).
- 4. History of myocardial infarction (MI) within the past three months.
- 5. Any concomitant arrhythmia or therapy that could interfere with the interpretation of the results from this study.
- 6. ASD closure device, LAA closure device, prosthetic mitral or tricuspid valve, or permanent pacemaker.
- 7. Any previous AF catheter ablation.
- 8. History of prior cardioversion for AF lasting > 48 hours.
- 9. Continuous AF episode lasting > 7 days immediately prior to the procedure without a sinus rhythm.
- 10. Severe electrolyte abnormalities at time of the ablation procedure or atrial fibrillation secondary to electrolyte imbalance, thyroid disease, or reversible non-cardiac cause.
- 11. Atrial fibrillation from a reversible cause (e.g., surgery, hyperthyroidism, pericarditis).
- 12. Contraindication to Heparin and Warfarin/other novel oral anticoagulants (e.g. dabigatran, rivaroxaban, apixaban).
- 13. History of pulmonary embolus within one year of enrollment.
- 14. Acute pulmonary edema.
- 15. Atrial clot/thrombus on imaging such as on a trans-esophageal echocardiogram (TEE) performed within 72 hours of the procedure if deemed appropriate by investigator.
- 16. History of a cerebrovascular disease (including stroke or TIA) within the last 12 months.
- 17. Any anticipation of cardiac transplantation or other cardiac surgery within the next 12 months.
- 18. History of thromboembolic event within the past 3 months.
- 19. Diagnosed atrial myxoma.
- 20. Significant pulmonary disease, (e.g. restrictive pulmonary disease, constrictive or chronic obstructive pulmonary disease) or any other disease or malfunction of the lungs or respiratory system that produces severe chronic symptoms and significantly increases risk to sedation or anesthesia.

21. Acute illness or active systemic infection or sepsis.
22. Known genetic bleeding disorders such as blood clotting abnormalities or bleeding abnormalities, not related to arrhythmia or the management of arrhythmia.
23. Life expectancy of less than 12 months.
24. Presence of intramural thrombus, tumor, or other abnormality that precludes catheter introduction or safe manipulation.
25. Women who are pregnant.

#### 7.2 INFORMED CONSENT

The investigator will obtain written informed consent from the subject using the EC-approved consent form prior to initiation of any study-specific assessments or procedures. Consent is documented by the dated signatures of the subject the person conducting the consent discussion, and the investigator. Written informed consent must be obtained from a potential subject no more than 90 days prior to performing the study procedure.

Informed consent completion will be monitored regularly by the sponsor.

#### 7.3 MOMENT OF ENROLLMENT

The subject will be considered "enrolled" in the study after the subject has met all inclusion and exclusion criteria, has signed the study informed consent form, and has completed the baseline assessments.

#### 7.4 RANDOMIZATION AND SUBJECT IDENTIFICATION

Randomization will occur if the subject is deemed eligible following screening baseline assessments and has signed the study informed consent form. Subject identification number will be assigned at the time of randomization and the identification number will be retained throughout the study. No personal identifying information will be included on the case report forms.

#### 7.5 SUBJECT DISCONTINUATION OR WITHDRAWAL

The investigator should instruct the subject regarding the importance of complying with the data collection and follow-up visit requirements. Poor subject adherence may result in the sponsor discontinuing the subject from the study.

Subjects may be involuntarily removed from the study for failure to adhere to the protocol, failure to attend follow-up visits, or due to safety reasons. In

such cases, the investigator shall arrange for an exit visit and complete a study exit case report form for the subject.

Subjects may voluntarily withdraw from the study at any time without reason. The investigator shall make an effort to obtain an exit visit but cannot insist on the visit if the subject does not wish to come in. The investigator shall complete a study exit case report form with as much information as is available at the time of withdrawal.

A subject may be withdrawn after screening and before receiving the study treatment if, at the investigator's discretion, he or she has developed a general health condition that would increase risks from study treatment.

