**Table 7 Follow-up (FU) Visit Windows**

Visit	Allowed Visit Date Range
Day 7 to 10 days (Phone or visit)	N/A
3 months (90 days)	± 2 weeks
6 months (180 days)	± 2 weeks
12 months (360 days)	± 4 weeks

- ***Resolution Period***

Following ablation treatment, subjects will undergo a 90-day “resolution” period (aka “blanking period”) where medical therapy may be optimized and where any of the procedurally-derived arrhythmias that commonly follow ablation procedures may resolve. During this period, adverse events will be accumulated but primary efficacy measurements will not be performed. In case of repeat ablation is solely for treatment of common type (cavo-tricuspid isthmus dependent) flutter, the patient has not failed the primary long-term efficacy endpoint.

*Note: During the 90-day resolution period, medications may be adjusted as medically indicated, and as indicated in above section. Any clinically indicated changes must be documented along with the reason for change.*

- ***Anti-arrhythmic Medications***

Anti-arrhythmic medications can be discontinued anytime from Day 91 to Day 180 post-procedure. The date of discontinuation will be determined by each investigator on a patient-by-patient basis, but must occur sometime from Day 91 to Day 180 post-procedure.

- ***Recurrence of AF***

If re-ablation for AF (not including common type atrial flutter) is necessary after documentation of the recurrent arrhythmia has

occurred, the patient will be considered a primary efficacy study failure but still followed up for AF burden.

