### 10 ADVERSE EVENTS

At enrollment, time of procedure, and at each post-procedure visit the subject will be evaluated for any complications or adverse event. The Investigator will be required to provide the Sponsor with any information concerning any findings that suggest any adverse events/complications pertinent to the investigation. All AEs occurring during the study will be recorded on the appropriate e-CRFs.

Subjects will be carefully monitored during the study for possible AEs. Any AE observed will be fully investigated by the Investigator and classified in line with the definitions below. All adverse events will be followed until resolution or until the Investigator judges the outcome to be chronic or stable.

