## 2.5 Missing Data and Lost to Follow-Up (Censoring)

No imputations or last observation carried forward (LOCF) will be conducted in this study. For purposes of the long-term primary safety and effectiveness endpoints, subjects missing safety or effectiveness data or lost to follow-up will be censored at their latest visit prior to the missing safety or effectiveness data.

For all other analyses, (acute safety and effectiveness), two presentations will be completed, one where the subject missing acute safety or effectiveness data or lost to follow-up will be excluded from the analysis, and another where that individual will be counted as a “failure” for the purpose of endpoint analysis. Both results will be presented.

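### Protocol 7.5 lets treated subjects be removed for non-adherence, missed visits or safety reasons; after a one-time procedure this only ends observation and creates avoidable, possibly informative censoring

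*Protocol*

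**What the plan says.** Protocol 7.5 gives two routes to removal without the subject's request. One is at the sponsor's hand: "Poor subject adherence may result in the sponsor discontinuing the subject from the study". The other is general: "Subjects may be involuntarily removed from the study for failure to adhere to the protocol, failure to attend follow-up visits", with safety reasons as a further ground. After such a removal, "the investigator shall arrange for an exit visit and complete a study exit case report form for the subject". The section names no later contact.

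The rule is not confined to the time before treatment. Follow-up visits can be missed only after the procedure, and withdrawal between screening and treatment has its own paragraph in 7.5.

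SAP 2.5 rules out imputation. For long-term effectiveness and long-term safety, "subjects missing safety or effectiveness data or lost to follow-up will be censored at their latest visit". Both endpoints use Kaplan-Meier estimates (Protocol 15.2 A and C; SAP 2.2.1 and 2.2.4). Only the acute endpoints get a second presentation, "another where that individual will be counted as a “failure” for the purpose of endpoint analysis".

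Three other passages bear on the point:

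- Protocol 10: "All adverse events will be followed until resolution or until the Investigator judges the outcome to be chronic or stable".
- Protocol 9.3, for subjects who need re-ablation for AF: "the patient will be considered a primary efficacy study failure but still followed up for AF burden".
- Protocol 12.4 classes medication non-compliance and follow-up outside the visit windows as minor deviations.

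**The concern.** In a drug trial, a discontinuation rule can serve to stop dosing. Here the intervention is complete on Day 0 (Protocol 9.3), so removing a treated subject changes nothing about the treatment received. It only stops data collection, on grounds such as medication non-compliance that 12.4 already handles as minor deviations.

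The grounds may be linked to outcome. A subject with returning symptoms may stay on anti-arrhythmic drugs longer than the plan allows, and a subject who is unwell may miss visits. What counts as adherence is also unclear. Section 9.2 D confines these drugs to the first three months, while 9.3 places their discontinuation between Day 91 and Day 180. Those passages must be reconciled.

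Censoring in a Kaplan-Meier analysis is harmless only if censored subjects have the same later risk as those who stay. If would-be failures are removed more often, freedom from AF/AT is overstated in the arm that loses them. If that happens more in one arm, the non-inferiority comparison shifts. Only subjects are blinded under Protocol 5, and SAP 1.1.6 says there is no masking, so a removal decision can be made with the arm known. One-year safety has the same weakness for events that begin after exit.

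**Working it through.** **1. The plan's own figure.** Inputs from Protocol 15.3: freedom 0.55 (FIRM) and 0.50 (PVI), margin 0.15, one-sided 95% limit, 80% power.

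n = (1.645 + 0.842)² × (0.55×0.45 + 0.50×0.50) / (0.55 − 0.50 + 0.15)² = 6.18 × 0.4975 / 0.04 ≈ 76.9, so 77 per arm, as stated. Exact binomial power with the Newcombe-Wilson limit is 80.6%. Adding 8 per arm gives 85, and 2 × 85 = 170. The plan's figure reproduces and is not in dispute here.

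**2. What happens to a removed subject.**

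| Data | Fate under the plan |
|---|---|
| Recurrence or procedure-related SAE documented by exit | Counts as an event |
| Adverse event known at exit | Followed to resolution or stability (Protocol 10) |
| New SAE after exit | No provision to collect it |
| Recurrence after exit, or not yet documented | No provision to collect it |
| Long-term endpoints | Censored at the latest visit before the missing data (SAP 2.5) |

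SAP 2.5 does not name removed subjects. They fall under its wording on missing safety or effectiveness data.

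**3. Size of the bias (worst case, assumed).** Take 85 per arm and true freedom 0.35 (FIRM) vs 0.50 (PVI), so the true difference sits at the margin. Suppose k FIRM subjects, all of whom would have recurred, are removed just after blanking, with no other censoring. Expected FIRM successes are 0.35 × 85 = 29.75, and the Kaplan-Meier estimate is about 29.75/(85 − k).

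**4. Effect on the decision.** Let FIRM successes be binomial (85 − k, 29.75/(85 − k)) and PVI successes binomial (85, 0.50). Non-inferiority is declared if the Newcombe-Wilson lower limit for FIRM minus PVI exceeds −0.15. Summing the exact probabilities gives:

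| k removed, FIRM only | Apparent FIRM freedom | Overstatement (points) | False non-inferiority, two-sided 95% CI | Same, one-sided 95% limit |
|---|---|---|---|---|
| 0 | 0.350 | 0 | 2.8% | 5.4% |
| 2 | 29.75/83 = 0.358 | 0.8 | 3.9% | 7.3% |
| 4 | 29.75/81 = 0.367 | 1.7 | 4.3% | 7.6% |
| 6 | 29.75/79 = 0.377 | 2.7 | 5.3% | 9.7% |
| 8 | 29.75/77 = 0.386 | 3.6 | 7.2% | 12.6% |

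Both interval types are shown because Protocol 15.2 A decides on a two-sided 95% interval and 15.3 sizes on a one-sided one. That mismatch is a separate matter.

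**5. Other patterns of removal.**

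- Equal k in both arms: at k = 8 the apparent difference is (29.75 − 42.5)/77 = −0.166, further from the claim than the true −0.15. Over k = 2 to 8, false non-inferiority is 2.7% down to 1.6% (two-sided) or 5.3% down to 3.3% (one-sided), so it does not rise.
- PVI only, k = 8: PVI freedom appears as 42.5/77 = 0.552 instead of 0.50. That bias of 5.2 points runs against FIRM.

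**The case against.** The strongest reply is that the protocol already protects much of the data. Removal is permissive, comes with an exit visit, and sits beside Section 7.6, which requires immediate contact and rescheduling after a missed visit. All of that is true, and it limits the damage. It does not supply follow-up after exit, which no section provides.

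Several stronger readings are tempting, and the documents do not support them:

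- **That 7.5 contradicts Sections 10, 9.3 and 15.1.** It does not. Section 10 makes no exception for removed subjects and so softens 7.5. The 9.3 rule covers only subjects re-ablated for AF. Section 15.1 defines the ITT set by randomization and catheter insertion, so a removed subject stays in the set and is censored, not excluded. The defect is avoidable missing data.
- **That a serious complication disappears when it leads to removal.** A procedure-related SAE is already an endpoint event by then and is reportable within 24 hours (Protocol 10.2). Only new, later events are lost.
- **That an unblinded investigator may remove subjects for poor adherence.** The adherence sentence names the sponsor. The general sentence is in the passive, and the investigator is assigned only the exit visit and form.
- **That about a third of the margin is at risk.** That figure needs eight would-be failures removed at true FIRM freedom 0.50: 42.5/77 = 0.552, or 5.2 points of 15. With PVI also at its assumed 0.50, a non-inferiority claim would be true. At the margin the figure is 3.6/15, about a quarter. The allowance of 8 per arm also covers all drop-outs and losses, not involuntary removals alone.
- **That the bias favours FIRM.** Nothing in the documents fixes the direction.

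**Conclusion.** The point holds as a defect in the conduct rule and its analysis. As written, the plan lets treated subjects leave observation for reasons that may relate to outcome. It then censors them for both long-term endpoints, with no planned analysis that would bound the effect.

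The size is unknown, because the documents give no removal rate, reason split or arm split. The FIRM-only range of 0.8 to 3.6 points, with false non-inferiority rising from 2.8% to about 4% to 7% (two-sided 95% CI), rests on three assumptions: every removed subject would have recurred, all left early, and only one arm was affected. Later or balanced removal does less or no harm to the error rate, and removal concentrated in PVI works against FIRM. The case for change is that the loss is avoidable and cheap to prevent, and that analysis cannot recover uncollected data. It is not that a false claim is likely.

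**What to change.** **Protocol 7.5.** State that once a mapping or ablation catheter has been inserted, non-adherence, missed visits or safety concerns do not end study follow-up. Observation ends only on withdrawal of consent, death, or loss to follow-up under 7.6. Non-adherence is recorded as a deviation under 12.4. Record the reason for every discontinuation and report reasons by arm.

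**Protocol 7.6.** At present three failed contact attempts make a subject lost. Amend it so that contact is tried again at each later scheduled visit through 12 months; otherwise it would undercut the change to 7.5.

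**Data collection after a subject stops attending.** Continue SAE, vital-status and rhythm collection to 12 months. Use the scheduled 72-hour Holter or CIED interrogation where the subject agrees, otherwise phone and medical records. Flag the latter as a different method of ascertainment: it will find mainly symptomatic, clinically documented episodes and cannot stand in for the planned monitoring.

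**SAP 2.5.** Extend the missing-as-failure presentation to long-term effectiveness and long-term safety as a sensitivity analysis.

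**Cost.** A wording amendment to both documents, modest extra contact effort at sites, and less complete rhythm data in subjects who stop attending. The sample size does not change.

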#### **7.6 CONTACT FOR FOLLOW-UP AND LOSS TO FOLLOW-UP**

Subjects who miss a study visit should be contacted immediately by the Investigational Site to determine the reason for the missed visit and to reschedule the visit as soon as possible to meet the study visit window. If the subject cannot be located after 3 attempts through a variety of communication modes (phone, email, letter), then the subject will be considered lost to follow-up. The investigational sites should collect contact information (home phone, cell phone, fax, email, home address, etc.) from the subject in order to minimize loss to follow-up. All attempts to contact the subjects will be documented and retained in the subject study record.

### **8 INVESTIGATIVE SITES**

Up to 20 investigational sites in Europe will participate in this study.

#### **8.1 INVESTIGATOR SELECTION**

- A. To qualify for participation, the study investigator will have completed the following:
  - o Undergone the standard training provided by Abbott EP (Topera, Inc.) in the use of the RhythmView® system and analysis of FIRMap® produced by the system
  - o Participated in 10 FIRM-guided procedures prior to enrolling any subjects in the study.

## 8.2 EQUIPMENT REQUIREMENT

A. In order to participate in this study, the site must also have the following equipment available:

- 64-pole mapping catheter (FIRMap Catheter) and appropriate analyzer to acquire full chamber data (RA or LA) per Abbott EP RhythmView system requirements.
- Abbott EP RhythmView 3D electrophysiologic mapping system.
- Optionally, 3-D electroanatomic mapping system (CARTO, Biosense Webster, Velocity or Nav-X, St Jude Medical) compatible with FIRMap for documentation of lesions relative to recordings from mapping catheter.

## 8.3 INVESTIGATOR DISCONTINUATION

[figure not shown]
Prior to participation in the study, all investigators must sign the Protocol Signature Page, which outlines the investigator's obligations in the study. The sponsor may elect to discontinue, or suspend, the investigator's participation in the study due to poor study compliance, lack of compliance with applicable regulations or EC requirements, or insufficient recruitment of study subjects.

## **9 STUDY FLOW AND VISIT SCHEDULE**

The study will be conducted in three phases listed below and depicted in Figure 1.

1. Screening & Baseline
2. Study procedure through discharge
3. Follow-up periods

Each of these phases is discussed separately below, following Table 5 – Schedule of Assessments.

**Figure 1 Study Flow**

\*EQ-5D QoL survey will be collected monthly post-procedure. Scheduling may be changed based on patient compliance.

FIRMAP AF  
Amendment 1  
Date: 15-December 2015

**Table 4 – Schedule of Assessments**

Event	Baseline	Procedure	Discharge	3-month	6-month	12-month
Informed consent	★					
Demographics, medical history, cardiac diagnosis	★					
Lab work, collected per institution's standard of care	★					
INR if patient is on Warfarin (as appropriate on post-procedure f/u)	★			★	★	★
TEE (when clinically indicated)	★					
Diagnostic 12-lead ECG	★		★	★	★	★
Documentation of symptomatic PAF	★					
Concomitant cardiac medications	★		★	★	★	★
NYHA Class Assessment	★					
EHRA Class Assessment	★					★
 EQ-5D QoL Survey	★			★	★	★
AFEQT QoL Survey	★			★	★	★
AF symptom and rhythm assessment	★		★	★	★	★
Ablation procedure		★				
AF interventional procedure(s) performed (repeat ablation, AF-related hospitalization)			☒	☒	☒	☒
AE assessment		★	★	★	★	★
72-hour ambulatory continuous ECG monitor (Holter) OR interrogation of CIED, as applicable	☒			★	★	★

 The ED-5D QoL survey will be completed on a monthly basis post index procedure. Scheduling may be changed based on patient compliance.

Legend: ★ = Required    ☒ = if applicable

## 9.1 SCREENING AND BASELINE

### A. *Screening*

Patients at the investigational sites with symptomatic paroxysmal AF will be asked about their interest in study participation. For those patients who express an interest to participate, the inclusion/exclusion criteria will be reviewed against existing medical history and the results of any standard clinical work-up to assess preliminary eligibility. Potential patients who do not meet entrance criteria may, as appropriate, repeat screening evaluations at a later time for possible enrollment into the study.

### B. *Baseline Assessment*

If the patient is not excluded on the basis of existing medical history and standard clinical work-up, the patient will be asked to provide informed consent to participate in the study. Baseline assessments include the following as shown in Table 5 – Schedule of Assessments.

- Determine study eligibility based on the requirements specified in the inclusion / exclusion criteria.
- Demographics.
- Medical history, including any hospitalizations or emergency room visits for episodes of all cardiac arrhythmias within six months of screening, all anti-arrhythmic drugs (AADs) and other cardiac medications.
- Reported incidence of at least two (2) documented episodes of symptomatic paroxysmal AF during the three months preceding trial entry (at least one episode should be documented by rhythm strip, CIED or ECG).
- Treatments administered for atrial fibrillation in the six months prior to enrollment, e.g., pharmacologic treatments and non-pharmacologic interventions. Medications should include dose and duration.
- Documentation of therapeutic International Normalization Ratio (INR) for three weeks prior to the procedure (if applicable per Inclusion Criteria) in cases of subjects taking warfarin.
- NYHA class.
- EHRA class.
- Current cardiac rhythm.
- Largest dimension left atrial diameter measured within the last 3 months or from transthoracic echo, cardiac CT or cardiac MR with image documentation. Intracardiac echocardiographic measurement at the time of the procedure can alternatively be used to document this.

- Ejection fraction (EF) measured within the last 3 months or from the pre-procedure TEE or TTE.
- When clinically indicated, TEE will be performed within 72 hours prior to the ablation procedure. If any evidence of left atrial thrombus is discovered, then the ablation procedure will not be performed at that time. The patient may be either excluded from the study or maintained on oral anticoagulation for an additional period of at least 6 weeks and re-tested (TEE repeated) for thrombi.
- If the patient has a preexisting CIED, interrogation of the device will be performed to document AF burden in the 1-2 months preceding the procedure.
- 12-Lead ECG within 72 hours of, or immediately prior to, study procedure.
- Cardiac medications currently prescribed for the subject's daily medical therapy.
- Laboratory values TSH, Electrolytes (sodium, potassium) and Creatinine
- Neurological Exam (if clinically indicated) if symptoms suggestive of neurologic disease, and is to be performed by the neurology medical staff.
- Prior to the procedure, anticoagulation therapy will be performed as per institutional standard.
- EQ-5D and AFEQT Quality of Life survey.

